The six-minute walk, physical activity level for up to 14 days, and the short physical performance battery will be measured prior to the start of this pilot study and these measures will be repeated at the end of this phase of the LITE Trial. Pain-free and maximal treadmill walking time may be measured before and after this weight loss + exercise intervention phase of the LITE Trial. Participants will be invited to return to the medical center to meet in a group with other participants and provide feedback to study investigators about their experience in this study. All participants from the pilot will be contacted over the phone and invited to participate in the focus group. The additional group visit will take approximately 60 to 90 minutes.

X. Potential problems and solutions. First, we recognize that a subset of PAD patients do not own computers or have home-internet capability. We have budgeted for the costs of a home computer tablet and internet capability for participants who require these. Additionally, low cost items that may help participants better adhere to study procedures may be purchased. Examples include chargers for telephones or computers, which will allow participants to communicate with the study coach. In no instance will the cost exceed \$50 per participant. Participants who provide a reason for poor adherence to study protocol (i.e. "I cannot take the study coaching telephone calls because I do not have a charger for my telephone") and if on further questioning the participant indicates that they cannot afford to purchase a charger, then study staff will potentially pay for this. With increasing availability of computer technology and internet access, we anticipate that our intervention will be accessible to the majority of PAD patients in the near future. *Second, we recognize that some PAD participants will change medication or undergo revascularization procedures during the LITE Trial. As in our previously completed randomized trials in PAD participants, we will systematically collect data on changes in medications and new revascularization procedures throughout the study. If there is imbalance regarding medication changes or revascularization procedures across the three study groups, we will repeat our analyses, adjusting for these changes. In our prior trials, medication changes and revascularization procedures have not meaningfully influenced our results.*

Some or all study measures may need to be repeated at baseline or follow-up testing for data quality purposes. In some cases, it may be necessary to take an additional, unscheduled blood pressure measurement. For instance, if a participant has high blood pressure during the ABI

PROTOCOL TITLE: Low InTensity Exercise intervention in PAD: The LITE Trial

and investigators would like to double check their arm pressure measurement before performing the six-minute walk either at the same visit or at a subsequent visit.

Determinations about blood pressure checks will be made on a case-by-case basis in consultation with [name] or [name] or other qualified personnel.

Y. Pilot Data Collection. *Some participants may be asked to complete a short questionnaire to allow investigators to better understand whether and how people with peripheral artery disease prefer to carry out walking exercise, and to collect data on whether weight loss is an important goal for people with peripheral artery disease.*

Z. Pilot Data Collection 2. To understand how people completing the LITE Trial metabolize nitrates, we will perform a preliminary study in which people who have completed follow-up testing are asked to drink one serving of “Beet It”, an all-natural beet root juice. This product is available for purchase on Amazon (<https://www.beet-it.com/product/beet-it-sport-shot/>). It contains 98% concentrated beet root juice and 2% lemon juice. Nutritional ingredients consist of 97 Kcal, 20 grams of carbohydrates, four grams protein, and 0.2 grams of total fat. Participants will be asked to attend a visit at the medical center after data collection for LITE is completed (this may often be an additional visit) and will be asked to drink one serving of the beet root juice (70 mL, 2.4 ounces). A blood draw will be performed prior to drinking the beet root juice and 2-3 hours after the participant consumes the beet root juice, for measurement of nitrates and nitrites. The amount of blood collected will be 16 ml total before and after consuming the beet root juice. Our goal is to determine the proportion of participants who achieve a concentration of nitrates of 400 nM after consuming the single serving of beet root juice. Variability has been demonstrated in metabolism of nitrate containing products, and we aim to determine inter-individual variability in metabolism in participants who have completed the LITE Trial.

AA. In follow-up to the above, and for exploratory aim #3, we will assess the acute effects of nitrate-rich beetroot juice, compared to placebo, on change in six-minute walk distance, four-meter walking velocity at usual pace, four-meter walking velocity at fast pace, and the SPPB. Participants who sign written informed consent will be assigned to either nitrate-rich beetroot juice, described above, a matching placebo that is made by the same company that does not include the nitrate-rich beetroot juice, or 10 minutes of light therapy with a 660 nm light. They will be asked to perform a six-minute walk, four meter walking velocity at usual and fastest pace, and the SPPB without consuming any beverage at the first visit for this substudy. Approximately 1-5 weeks later, they will return for repeat measures. However, prior to the repeat measures, performed approximately 1-5 weeks after the initial measure, they will either consume one drink of nitrate-rich beetroot juice, consume the matching placebo, or receive light therapy. Blood will be obtained prior to the intervention (drink or light therapy) and at approximately 2.5 hours after ingesting the drink or 10 minutes after the light therapy. The blood will be obtained for measurement of nitrate and nitrite and potentially other blood measures for research. Participants assigned to light therapy will receive up to 10 minutes of light therapy with a 660 nm light (<https://mitoredlight.com/products/mitomid>) prior to the second blood draw at the second visit. The six-minute walk, the four-meter walk at usual and fastest pace, and the SPPB will be performed immediately after the blood draw. Participants may be asked to return for a third visit, in which they receive both nitrate-rich beetroot juice and the light therapy. At this third visit, participants will undergo a blood draw. They will then receive the nitrate-rich beetroot juice. Approximately 2.5 hours later, they will receive the 10 minutes of light therapy. Immediately after the light therapy they will have plasma measured for nitrite and they will undergo

PROTOCOL TITLE: Low InTensity Exercise intervention in PAD: The LITE Trial

functional performance measures (six-minute walk, four meter walks, and SPPB) immediately after the blood draw. In statistical analyses, the degree of change in each outcome (six-minute walk distance, four-meter walking velocity at usual pace, four-meter walking velocity at fastest pace, or the SPPB) between the initial measure and the measure obtained approximately 1-5 weeks later after consumption of the study drink and/or the light therapy, will be assessed and compared with those who received placebo. We will also analyze the association between the combination of the therapies (nitrate-rich beetroot juice + light therapy) and the individual therapies for the outcomes of increases in plasma nitrite and the degree of improvement in the functional measurements.

Specimens may be shipped to Wake Forest University for measurement of nitrates and nitrites, for participants who agreed to the optional beetroot juice portion of the study.

Procedures performed to lessen the probability or magnitude of risks.

A. Adequacy of protection against risks and methods to minimize potential risks. *Overview of protection against risks.* Prior to beginning data collection, all study coordinators undergo training and are certified by [name] using a detailed checklist for each data collection element (see Appendix C). Research coordinators are certified in each element of the study visit including obtaining informed consent, administering questionnaires, protecting confidentiality of collected data, performing the six-minute walk, and performing the ankle brachial index. [name] re-certifies coordinators every six months to ensure continued adherence to protocol. Those not adhering to all aspects of the protocol undergo additional training followed by re-certification.

All research staff members have completed human subjects training required by Northwestern's institutional review board (IRB). This training includes education about the importance of maintaining confidentiality of personal health information. The study principal investigator or a co-investigator is available to answer questions that arise during the informed consent process as needed.

Participants are asked to sign a study consent form at each on-site visit. The research coordinator reviews study procedures, including risks and benefits associated with study participation. The research coordinator answers participants' questions. [name] and other study investigators are available to answer participants' questions. Both the participant and the individual administering the consent form will sign the consent form. [name] pager, direct telephone line, and home telephone number are provided to participants.

B. Minimizing risks related to exercise. According to current clinical practice guidelines (1), all participants will undergo baseline exercise stress testing prior to randomization. Potential participants with an abnormal baseline exercise stress test will be excluded. A safety manual will be developed prior to beginning the exercise intervention and will be reviewed and approved by the Data Safety Monitoring Board (DSMB) before implementation. In addition, participants will be monitored during supervised exercise for development of chest discomfort, new dyspnea, or new fatigue during exertion. [name] will be promptly notified when this occurs (by pager). Our exercise physiologists have significant experience working with populations of participants with PAD and have been trained in CPR, ACLS, and use of the automatic external defibrillator. During transition to the home-based exercise program, participants are educated on important symptoms to watch for during exercise, such as chest discomfort or dyspnea. Participants are instructed to

PROTOCOL TITLE: Low InTensity Exercise intervention in PAD: The LITE Trial

immediately contact their physician should these symptoms occur. During their first on-site exercise session, the coach discusses information regarding safety during exercise. [name] cellular telephone number, pager, and direct line are provided in the informed consent form so that they can reach [name] easily with any questions or concerns.

C. **Minimizing risks related to muscle biopsy.** The muscle biopsy procedure will be performed by [name] who has more than 30 years of experience performing these muscle biopsies, primarily as part of his clinical practice as a Board-Certified Neurologist. As in our pilot study, completed in preparation for this proposal, the muscle biopsy procedures will be performed under sterile conditions using sterile technique. Local anesthesia will be obtained using subcutaneous lidocaine. All participants will be provided with written and verbal instructions about wound care and will be advised to contact [name] immediately if any signs of wound infection occur. All participants will return for a one-week follow-up check of their incision site.

Many PAD participants take anti-platelet therapy to prevent cardiac and cerebrovascular events. If potential participants are taking anti-platelet therapy, they will be asked to either hold their anti-platelet therapy (if they are taking 81 mgs of aspirin or less per day) or switch to a low dose (81 mgs) of aspirin therapy (if they are taking clopidogrel or an equivalent medication or > 81 mgs of daily aspirin at study entry) during the seven days leading up to the muscle biopsy procedure. Participants who are taking warfarin or other anti-coagulant therapy will be excluded from the muscle biopsy procedure.

D. **Minimizing risk related to baseline and follow-up testing.** All study coordinators undergo baseline training and are certified by [name] before beginning data collection. Training and certification involves ensuring that coordinators are trained in methods to help minimize falls. [name] re-certifies coordinators every six months to ensure continued adherence to study protocol. Those who are not adhering to protocol undergo additional training followed by re-certification.

E. **Minimizing risk related to loss of confidentiality.** The following methods will be employed to maintain confidentiality of participants. First, study recruitment letters will be mailed, using IRB-approved methods, only after receiving written permission from the participant's physician. The personal physician of each study participant will have the option of **not** allowing investigators to contact the potential participant. Lists of potentially eligible participants will be obtained by individuals who normally have access to these lists as part of their daily work requirements. Recruitment letters for potential participants identified from hospital and outpatient lists are prepared by research staff members whose job is to assist study investigators with recruitment. These research staff members have completed training in the ethical conduct of human subject research, including maintaining participant confidentiality. Recruitment letters to potential participants identified from medical center lists are mailed in sealed envelopes and addressed to the potential participant. All potential participants who receive mailed information about the study after the approval from their physician will have the opportunity to call a voice-mail system to ask NOT to be further contacted about this study. Secondly, only study investigators and key research staff will have access to the study database. Third, participants will be assigned a unique study identifier. Individual names will ultimately be removed from the study database and only the unique study identifier will be used to distinguish participants in the database. Fourth, collected data will be

PROTOCOL TITLE: Low InTensity Exercise intervention in PAD: The LITE Trial

maintained in locked computer files and file cabinets to which only study investigators have access. Collected data will be used only for research purposes. Any published data will not contain any individual identifiers.

F. **Minimizing risk related to loss of confidentiality during qualitative interviews.** Participation includes a risk of loss of confidentiality regarding personal health information. However, all research staff have undergone formal human subjects training. They are trained to protect the privacy of research subject participants. *Each qualitative interview will be digitally recorded to reduce the need for note taking and to facilitate analysis. When participants consent to the study, we will use a staged consent to ask permission to record the qualitative portion of the interviews to better capture qualitative data. If a participant does not give permission for audio-recording, s/he can still participate in the study. In those cases, the designated interviewer will enter as much of the participant's responses as possible. Digital recordings of the interviews will be permanently erased from the server five years following the end of the data collection period. We will retain de-identified transcripts of participant responses.*

G. **Minimizing risk related to the weight loss intervention.** Individuals who lose > 1.36 kilograms per week for three weeks in a row will be contacted by study staff. Calorie goals will be increased and [name] will interview the participant to determine whether additional medical evaluation is warranted. Second, to avoid dehydration, participants will be advised early on in the trial of the importance of maintaining adequate hydration. Participants will be reminded regularly of the importance of adequate hydration.

H. **Data and Safety Monitoring Board (DSMB).** As per NHLBI guidelines, the DSMB will be appointed by the NHLBI. The DSMB will meet at least every six months during the study. The DSMB will meet to review and approve the protocol prior to beginning data collection. They will decide on specific stopping criteria for the study. The biostatisticians and data manager will work closely with the DSMB to perform interim analyses. Adverse events and hospitalizations will be monitored monthly via telephone call and will be reported to the DSMB and IRB in a timely manner according to pre-specified requirements. Analyses will be done according to the requests of the DSMB. In addition, for each major adverse event, the group assignment of the patient will be provided. In this way the DSMB can determine whether the event is intervention related. Adverse event rates and interim study results will be reviewed and discussed by the DSMB at the DSMB meetings. At least four categories of adverse events will be defined: a) Death; b) cardiovascular events (myocardial infarction, stroke, and coronary arrhythmias) c) musculoskeletal outcomes (muscle soreness, foot ulcer, joint aches and pains). We will also include adverse events for the muscle biopsy, including a) infection and b) bleeding requiring a visit to a healthcare provider. We will report all hospitalizations to the DSMB in a timely fashion. We will use a designated data collection form to record these events and they will be reported immediately to the Institutional Review Board and DSMB. Note that to date, however, exercise programs have been demonstrated to be safe in patients with PAD (1,52,55).

- *All drugs and devices used in the research.*

PROTOCOL TITLE: Low InTensity Exercise intervention in PAD: The LITE Trial

Participants will be asked to wear the ActiGraph while they are exercising. The ActiGraph records duration, frequency, and intensity of exercise. The ActiGraph Bluetooth mechanism, available in the ActiGraph model that we will use in the LITE Trial, automatically uploads data to the study website, whenever participants walk within 15 feet of their home computer/tablet. Participants without a home computer suitable for uploading ActiGraph data will be provided with a computerized tablet with wireless internet access for the duration of the study.

- *Source records that will be used.*

Sources of material. Primary and secondary outcome measures that will be collected for this study are shown in Table 7 and include the six-minute walk test, treadmill walking performance, physical activity measured by the ActiGraph accelerometer, calf muscle biopsy measures, quality of life questionnaire data (SF-36 PF score), and patient-perceived walking ability (WIQ scores). In addition, adherence to the prescribed exercise intervention will be measured during the final four weeks of the intervention in the two exercise groups using the ActiGraph. Qualitative interviewing will be conducted to obtain information about participants' perceptions of their walking exercise experience. We will also administer questionnaires to participants at baseline and at each follow-up visit to assess their medical history, including presence of comorbidities, medication use, smoking status, and other health characteristics. Data collection will not make use of existing records or data. The prevalence of comorbid disease will be measured using patient report, based on previous study (98-101).

9.3 *Data collected.*

Please see section 9.2 above.

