2. Individuals whose walking is limited by a condition other than PAD.	2. The intervention is designed to improve PAD-related walking impairment.
3. > Class II NYHA heart failure or angina. Increase in angina, angina at rest, or abnormal baseline treadmill stress test.	3. Exercise may not be safe for these potential participants.
4. Major surgery including lower extremity revascularization or orthopedic surgery during the prior three months or anticipated in the next twelve months.	4. Surgery may influence change in functional performance, independent of study interventions.
5. Major medical illness including renal disease requiring dialysis, lung disease requiring oxygen, or cancer (other than non-melanoma skin cancer) requiring treatment in the prior three years. Note: Potential participants may still qualify if they have had treatment for an early stage cancer in the past three years and the prognosis is excellent. Patients who use oxygen at night may still qualify.	5. These conditions may interfere with the ability to fully participate and complete the study.
6. Mini-mental status examination score <23 (63), dementia, or psychiatric illness including severe depression or anxiety. However, investigator discretion may be used to allow some people with an MMSE below this threshold to participate, if the investigator determines there is another reason for their lower score, including lack of sufficient familiarity with the English language or lack of sufficient education to achieve a score of 23 or higher. Note that the MMSE includes some spelling and English writing proficiency.	6. May interfere with ability to fully engage in the study.
7. Currently walking regularly for exercise at a level comparable to the amount of exercise prescribed in the intervention.	7. The interventions may not further improve functioning.
8. Currently enrolled in another clinical trial, exercise trial, or in cardiac rehabilitation. Currently enrolled in a clinical trial or participation in cardiac rehabilitation or a	8. Interference with ability to determine whether study interventions are responsible for improved outcomes.

PROTOCOL TITLE: Low InTensity Exercise intervention in PAD: The LITE Trial

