11.0 Data and Specimen Management

11.1 Data analysis plan.

- A. **Data management.** We will use data management methods in place for our ongoing NHBLI-funded PAD studies. Data from baseline and follow-up study visits are acquired on paper forms and processed using the Teleform system by Cardiff Software. We have successfully used this system for over 8,000 patient visits in our previous and ongoing studies. Data are backed-up on multiple hard drives and copied to CDROM for secure off-site storage.
- B. **Data Safety Monitoring Board (DSMB).** We have identified nationally recognized experts to serve on the DSMB.

Statistical Analyses. Analyses will be performed according to the intention to treat principle. Data will be analyzed according to each participant's originally assigned group, irrespective of whether the participant adheres to his/her assignment. Prior to analyses, the distributions of the variables (changes) will be examined and necessary transformations will be performed. The balance of socio-demographic factors and prognostic factors (such as age, sex, race, ABI, comorbidities, and relevant medication use) will be compared between the three groups using ANOVA or chi-square tests. If there is any indication of major imbalance, proper analysis of covariance adjustments will be performed in data analyses.

NOTE: The original plan to use two sample two-tailed t-tests was changed to a mixed model for repeated measures analysis on 8/27/2020 prior to analyzing any data. This change was made because as of 8/27/202, investigators are projecting an approximately 16% loss to follow-up rate at 52 week follow-up. The mixed model for repeated measures will be used to adjust for missing data.

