For our Primary Aim, we will use mixed model for repeated measures (MMRM) analysis to compare changes in six-minute walk performance at 52-week follow-up between the low vs. the high-intensity exercise group and between the low-intensity exercise group vs. the control group, respectively. To this end, the 26-week and 52-week changes of six-minute walk from baseline are treated as correlated outcomes, and independent variables include visit (26-week and 52 week), treatment (low-intensity, high-intensity, control), visit/treatment interactions and baseline six-minute walk performance. Unstructured variance-covariance matrix will be used to model the within-person correlations. In addition, we will also adjust for potentially imbalanced baseline confounders such as age, sex and baseline six-minute walk performance. When there is evidence that the normality assumption for the distribution of measures of interest is severely violated, we will perform Wilcoxon rank-sum test for the comparison. The nonparametric adjustment for the imbalance in mean difference of baseline covariates will be employed, when needed.

PROTOCOL TITLE: Low InTensity Exercise intervention in PAD: The LITE Trial

For Secondary Aim #1, we will use MMRM analysis to compare changes in six-minute walk, physical activity, and SF-36 PF and WIQ distance and speed scores at 26-week follow-up between the low- and high-intensity exercise groups and between the low-intensity exercise and control group, respectively.

For our Secondary Aim #2, we will use MMRM analysis to compare changes in maximal treadmill walking time, physical activity, and SF-36 PF and WIQ distance and speed scores at 52-week follow-up between the low- and high-intensity exercise groups and between the low-intensity exercise and control groups, respectively.

For our Secondary Aim #3, we will use normal approximation for binomial distribution to compare the proportion of participants who achieve adherence (as defined in section C18) between the low vs. high intensity exercise groups. We will also use logistic regression to compare the adherence rate between these two groups, adjusting for potentially imbalanced baseline confounders such as age, sex, and baseline six-minute walk performance. We will also use two sample two-tailed t-tests to compare adherence to the exercise intervention overall and at the prescribed intensity between the high vs. low intensity groups at 52-week follow-up.

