Power estimates. For all primary and secondary aims, we anticipate a 15% drop-out rate at 52-week follow-up, based on 12-month follow-up rates in our GOALS and SILC trials (52,55). We will randomize 305 participants. Of these, 120 will be randomized to the low-intensity intervention, 120 will be randomized to the high-intensity exercise intervention, and 65 will be randomized to the control group. We will enroll more participants in each exercise group than the attention control group because we anticipate that the effect size of the low vs. high intensity exercise comparison will be lower than the effect size of the low intensity vs. the control group. For our Primary Specific Aim, we will have 80% power to detect a minimum difference of 0.43 standard deviations (SD) between the low intensity vs. high intensity exercise groups and a difference of 0.52 SD between the low-intensity and the attention control groups, in change of six-minute walk distance at 52-week follow-up, using two-sided two-sample t-tests **with a significance of 0.025 to adjust for the two comparisons.** Low intensity exercise will be considered effective if either comparison (i.e. with high intensity exercise or with the attention control group) is statistically significant. The SD of the change in six-minute walk in our GOALS and SILC trials was approximately 60 meters. Therefore, our sample size allows us to detect a difference in change in six-minute walk of 26 meters and 31 meters, respectively, between the low vs. high intensity groups and between the low intensity and control groups. Prior studies have defined clinically meaningful changes in the six-minute walk as 30 meters (small meaningful change) and 50 meters (large meaningful change) (102,103). Thus, our power should be adequate to detect a clinically meaningful difference. For our Secondary Aim #1, we will have 80% power to detect a difference of 0.39 SD between the high vs. low intensity exercise interventions and a difference of 0.47 SD between the low-intensity intervention vs. control group, respectively, in changes of six-minute walk, physical activity, WIQ scores, and SF-36 scores at 26 –week follow-up using two-sided two-sample t-tests with a significance of 0.05. For our Secondary Aim #2, we will have 80% power to detect a difference of 0.39 SD between the high vs. low intensity exercise interventions and a difference of 0.47 SD between the low-intensity intervention vs. control group, respectively, in changes of maximal treadmill walking time, physical activity, and WIQ and SF-36 scores at 52-week follow-up, using two-sided two-sample t-tests with a significance level of 0.05. In our SILC trial, the observed differences between the intervention and control groups are 0.61 SD, 0.59 SD and 0.61 SD in changes of maximal treadmill walking time, WIQ distance, and SF-36 physical functioning scores, respectively (52). In a study by Gardner et al of supervised exercise in participants with PAD (73), the observed improvement in physical activity

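### If on-study medication changes or revascularisations differ by arm, the plan repeats its analyses adjusted for these post-randomisation events, and that repeat does not estimate the intention-to-treat effect.

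*Combined protocol and SAP*

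**What the plan says.** Section 9.2, X, expects some participants to change medication or be revascularised during the trial and promises that "we will systematically collect data on changes in medications and new revascularization procedures throughout the study". It then gives the rule: "If there is imbalance regarding medication changes or revascularization procedures across the three study groups, we will repeat our analyses, adjusting for these changes". The reassurance offered is "In our prior trials, medication changes and revascularization procedures have not meaningfully influenced our results", without figures.

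The main analysis in section 11.1 is of a different kind: "Analyses will be performed according to the intention to treat principle". The primary mixed model for repeated measures (MMRM) uses visit, arm, their interaction and baseline walk, and its further adjustment is confined to baseline: "In addition, we will also adjust for potentially imbalanced baseline confounders such as age, sex and baseline six-minute walk performance".

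For the repeat analysis the documents give no criterion for imbalance, no coding or timing of the events, no estimand, and no rule for reading a result that disagrees with the main one.

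**The concern.** Randomisation protects comparisons adjusted for variables fixed at baseline. It does not protect comparisons adjusted for events that happen later. The arms are walking to ischaemic pain, walking comfortably and no exercise, so leg symptoms may evolve differently, and with them revascularisation and drug changes. If assignment affects these events, adjustment does two things. It removes whatever part of the effect passes through the event. It also compares people alike on the event but unlike on the unmeasured worsening that led to it.

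The trigger makes this worse, because adjustment is harmless when the events are balanced and the rule applies when they are not. This is the plan's stated response to co-interventions that differ by arm. If the adjusted and unadjusted results disagree, the reader cannot tell whether a co-intervention explains the walking result or the adjustment has produced the difference.

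**Working it through.** **1. The plan's own scale (section 11.2).** Inputs: "Of these, 120 will be randomized to the low-intensity intervention, 120 will be randomized to the high-intensity exercise intervention, and 65 will be randomized" to control; 15% drop-out; two-sided 0.025; 80% power; "The SD of the change in six-minute walk in our GOALS and SILC trials was approximately 60 meters".

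- Evaluable: 120 × 0.85 = 102 per exercise arm; 65 × 0.85 = 55.25 controls.
- Normal approximation: (2.241 + 0.842) × √(2/102) = 0.43 SD, and 3.083 × √(1/102 + 1/55.25) = 0.515 SD. The exact t-test gives 0.434 and 0.519, which reproduces the stated 0.43 and 0.52.
- In metres: 0.43 × 60 = 25.8 and 0.52 × 60 = 31.2, the plan's 26 m and 31 m.

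**2. Formula for the shift.** Let M mark an on-study event, with proportions p1 and p0 in the two arms, and let b be its coefficient in the adjusted linear model. Then

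adjusted − unadjusted = −b × (p1 − p0).

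If p1 = p0 the shift is zero whatever b is.

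**3. Range.** Event rates and effects are assumptions. Large-sample simulation, outcome SD about 60 m, true total effect 31 m:

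| Assumed mechanism | p1 v p0 | b (m) | −b × (p1 − p0) | Unadjusted → adjusted (m) |
|---|---|---|---|---|
| Event adds 40 m, no shared cause | 5% v 20% | 40.2 | +6.0 | 31.1 → 37.1 |
| Same | 1.6% v 5% | 39.9 | +1.4 | 30.8 → 32.2 |
| No event effect, shared worsening | 7.9% v 20% | −38.8 | −4.7 | 31.1 → 26.4 |
| Same | 2.3% v 5% | −47.7 | −1.3 | 31.1 → 29.8 |
| Both | 7.9% v 20% | 1.2 | +0.1 | 31.1 → 31.3 |

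Across the imbalanced scenarios run, the first mechanism gave +1.4 to +6.1 m, the second −1.3 to −4.7 m, and both together about −0.3 to +0.2 m. With equal rates the shift was about 0.

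**4. A harsher case.** Suppose worsening correlates 0.6 with the walk (0.6 × 60 = 36 m per SD), the procedure has no effect, and everyone beyond a threshold of worsening is revascularised. With φ(p) the normal density at the cut-off for proportion p:

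b = −36 × [φ(p1) + φ(p0)] / [p1(1 − p1) + p0(1 − p0)].

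- 4% v 10%: b = −36 × (0.0862 + 0.1755)/(0.0384 + 0.0900) = −73.4; shift = 73.4 × (−0.06) = −4.4 m.
- 6% v 15%: b = −36 × (0.1191 + 0.2332)/(0.0564 + 0.1275) = −69.0; shift = 69.0 × (−0.09) = −6.2 m.

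If the event depends only loosely on worsening, b scales with that link. At a link of 0.5 the shifts halve to −2.2 and −3.1 m.

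**5. Would discarding post-event walks cure it?** In the case of step 4 with no true effect, simply dropping those walks leaves 36 × [φ(p1)/(1 − p1) − φ(p0)/(1 − p0)]:

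- 4% v 10%: 36 × (0.0898 − 0.1950) = −3.8 m.
- 6% v 15%: 36 × (0.1267 − 0.2743) = −5.3 m.

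Imputing them from the 26-week change leaves about −1.4 to −2.9 m by simulation. That assumes a correlation of 0.7 between the 26- and 52-week changes, a correlation of 0.42 to 0.6 in size between worsening and the 26-week change, and a 26-week walk for everyone. This is better than adjustment but not free of bias.

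**The case against.** **Only an extra run is affected.** This stands. The confirmatory result is the intention-to-treat MMRM with baseline covariates, tested at 0.05/2. A reader might infer that the primary result is biased; sections 11.1 and 11.2 give no support for that. Nor do the documents say that the repeat run would overrule the main one.

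**An imbalance may be chance.** This also stands. A reader might infer that any arm difference in these events must be an effect of treatment. With 102 per arm and a common 7% rate (assumed), a gap of six or more events in either direction arises by chance about 13% of the time (binomial calculation). If assignment truly had no influence on the events, adjusting for them would not be objectionable on this ground. But an imbalance check cannot separate the two cases, and the rule treats them alike.

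**The events may be unrelated to the intervention, or rare.** Table 3 (section 3.2) justifies excluding recent or anticipated surgery with "Surgery may influence change in functional performance, independent of study interventions". That supports an entry criterion; it does not show that later procedures are independent of arm. The exclusion should lower event rates, but no rates are given. The statement about prior trials carries no figures.

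**The harsher figures overstate.** From step 4 a reader might infer that about a fifth of a 26 m effect would be lost (4.4/26 = 17%; 6.2/26 = 24%). That needs revascularisation to be fixed entirely by worsening and to bring no benefit. The documents support neither condition, and other assumptions reverse the sign or cancel the shift.

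**Conclusion.** The concern holds for the conditional repeat analysis and no further. Adjusting for on-study medication changes or revascularisations gives an estimate that differs from the intention-to-treat effect in proportion to the imbalance that triggers it, and that has no clear causal meaning. That much follows from the stated rule and the linear-model identity.

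The size does not follow from the documents. Under the assumed rates and effects above it is about 0 to 6 m in either direction, at most roughly a fifth to a quarter of the 26 m and 31 m targets, and it can cancel. The simulations treat one yes/no event in a linear model. Medication changes were not modelled separately, and their coding is unspecified. Because the sign cannot be known in advance, this run can neither confirm nor refute the main result. It is a moderate flaw in a robustness check and worth correcting.

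**What to change.** In section 9.2, X, delete the imbalance-triggered covariate adjustment. State that the intention-to-treat (treatment-policy) MMRM is the reference result whatever co-interventions occur, and that medication changes and revascularisations will be tabulated by arm.

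If a supplementary analysis of revascularisation is wanted, pre-specify it as a separate estimand with a hypothetical strategy: six-minute walks after the procedure are set to missing and imputed from baseline and 26-week data, with a stated range of delta values. The delta range is needed because these walks are probably not missing at random and step 5 shows that some bias remains. Section 11.1 already names multiple imputation and pattern-mixture models, so little new method is required. Medication changes would be tabulated only.

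Confirm that procedure dates are recorded; the protocol promises data on procedures but does not mention dates.

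The cost is about one paragraph of text. The downside is slightly more missing data and an untestable assumption, both confined to the supplementary analysis.
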